2.2.4 Selected Other Endpoints/Variables

2.2.4.1 Map Detection Endpoints/Variable

Mycobacterium avium subsp. paratuberculosis (MAP) detection parameters include the following with baseline defined as week 0 of the open label phase:

-
- Proportion of subjects with positive MAP buffy coat culture at baseline, weeks 26 and 52.
 - Proportion of subjects with a change in MAP buffy coat culture after 26 and 52 weeks of treatment compared to baseline.

2.2.4.2 Endoscopic Change Endpoint/Variables

- Change from baseline to week 16 and 52 in Crohn's Disease Endoscopic Index of Severity (CDEIS) and Simple Endoscopic Score for Crohn's Disease (SES-CD). The CDEIS and SES-CD are endoscopic scoring systems for the assessment of CD.
- Success rate by 25% improved in CDEIS from baseline to week 16 and 52. Success is achieved if the CDEIS score is decreased by 25%.
- Success rate by 50% improved in CDEIS from baseline to week 16 and 52. Success is achieved if the CDEIS score is decreased by 50%.
- Success rate by 25% improved in SES-CD from baseline to week 16 and 52. Success is achieved if the SES-CD score is decreased by 25%.
- Success rate by 50% improved in SES-CD from baseline to week 16 and 52. Success is achieved if the SES-CD score is decreased by 50%.
- Comparison of success rate of by 25% and 50% improved in CDEIS from baseline to week 16 and 52 vs CDAI defined remission.
- Comparison of success rate of by 25% and 50% improved in CDEIS from baseline to week 16 and 52 vs CDAI defined response.
- Comparison of success rate of by 25% and 50% improved in SES-CD from baseline to week 16 and 52 vs CDAI defined remission.
- Comparison of success rate of by 25% and 50% improved in SES-CD from baseline to week 16 and 52 vs CDAI defined response.

2.2.4.3 Health Related Quality of Life Endpoint/Variables

- The Short Form-36 Health Survey (SF-36) domain and component scores at week 16 and 52.
- Change from baseline in the total IBDQ score to week 16 and 52. Inflammatory Bowel Disease Questionnaire (IBDQ) score is designed to measure effects of subject's inflammatory bowel disease on their daily functions and quality of life during last 2 weeks.

2.2.4.4 Markers of Inflammation Endpoint/Variables

Inflammation parameters include the following:

- Change from baseline in C-reactive protein (CRP)
- Change from baseline in fecal calprotectin

2.2.5 Safety Endpoints/Variables

Safety parameters include the following:

- Incidence of adverse events
- Laboratory parameters (hematology, chemistry, urinalysis)
- Clostridium difficile toxin
- Vital signs
- ECG
- Physical examination
- Concomitant medications

3. STUDY DESIGN

This is an open label, multicenter, Phase III, study designed to evaluate the efficacy and safety of RHB-104 to treat subjects with active CD as defined by CDAI \geq 150 despite 26 weeks of treatment with study drug in RedHill Biopharma Study RHB-104-01. RHB-104 consists of 3 antibiotics with activity against *Mycobacterium avium subsp. Paratuberculosis* (MAP), a potential cause of CD. Eligible subjects with active CD who have completed 26 weeks of study drug as part of the RHB-104-01 study will receive up to 52 weeks of open label RHB-104. Subjects enrolled in the open label study may have current CD therapies adjusted or withdrawn as clinically indicated by their local investigator after 8 weeks of open label RHB-104 treatment. Sites should begin tapering steroids upon completion of 4 weeks of RHB-104 treatment with the goal of being steroid free by week 14 – Refer to Appendix 13 of protocol.

MAP are slow growing mycobacteria without a proven antibiotic treatment, and the duration of antibiotic treatment required to achieve remission in subjects with CD caused by MAP is believed to be approximately 16-26 weeks. Subjects with response at week 26 may ultimately achieve remission at a later time point with continued treatment for MAP. Similarly, some subjects may achieve response or achieve remission prior to week 26. This study is designed to assess response, remission, and maintenance of remission in subjects on open label RHB-104 through week 52, as well as corticosteroid free remission at week 16.

Blood samples will be collected at Screening and at every visit after the initial 8 weeks of treatment to test for MAP in the serum using a polymerase chain reaction (PCR) assay. Similarly, MAP cultures will be prepared from whole blood collected at Screening and at weeks 16, 26 and 52.

Safety of the fixed-dose combination product, RHB-104, will also be assessed.

Colonoscopy will be done in consenting subjects at baseline and after 16 and 52 weeks of open label RHB-104 to assess for mucosal healing as well as MAP status via PCR and culture.

4. SCHEDULE OF ASSESSMENTS AND TREATMENT ASSIGNMENT

4.1 Schedule of Assessments

Appendix 1 provides reference information from eCRF guidelines about subject data migration from the parent study.

The study schedule is summarized in the study visit schedule table on next page.

4.1.1 Study Visit Schedule

	Screening / Opt Screening / Visit Week 26 of RHB-104-01	Baseline Day 1 / Week 0 ²	Week 2	Week 4	Week 8	Week 16	Week 26	Week 39	Week 52	Week 56
Study Visit Window	(up to 21 days before BL if initial colonoscopy is performed)	Up to 21 days post SCR	± 3 days	± 3 days	± 7 days	± 7 days	± 7 days	± 7 days	± 7 days	± 7 days
Informed Consent	X									
Inclusion/ Exclusion Criteria Demography, Medical History	X	X								
Concomitant Medications Assessment		X ³	X	X	X	X	X	X	X	X
Vital Signs and Physical Exam.	X ¹	X	X	X	X	X	X	X	X	X
Adverse Event Assessments		X ³	X	X	X	X	X	X	X	
Diary Dispensing (AE/ConMed)		X	X	X	X	X	X	X	X	X
Steroid Status		X				X	X	X	X	X
CDAI assessment	X ¹				X	X	X	X	X	X
CDAI Diary Dispensing ⁴					X	X	X	X	X	
Subject Assessments: IBDQ and SF-36	X ¹					X	X		X	
Uveitis Assessment	X ¹		X	X	X	X	X	X	X	X
ECG ¹⁰	X ¹			X		X			X	X
Hematology and Biochemistry	X ¹		X	X	X	X	X	X	X	X
Urinalysis ¹¹	X ¹		X	X	X	X	X	X	X	X
C-Reactive Protein (CRP)	X ¹					X	X	X	X	
MAP Testing Blood (PCR) with Add'l Sample for Future Use	X ¹				X	X	X	X	X	X
MAP culture from blood	X ¹					X	X		X	
Fecal calprotectin	X ¹					X	X		X	
C. difficile Testing	X ¹						X		X	
Pregnancy Test Urine	X ¹	X	X	X	X	X	X	X	X	X
Optional Colonoscopy and CDEIS/SES-CD; store images		X ⁴				X ⁵			X ⁶	
IWRS Entry		X ⁷		X ⁸			X ⁹			
Study Drug Dispensing		X	X	X	X	X	X	X		
Dispensing of Drug Administration Instructions ¹²		X	X							
Drug Return & Accountability		X ¹³	X	X	X	X	X	X	X	
Review of stool sampling technique					X	X		X		
Telephone reminder of dose escalation		Day 7	Day 21							

¹ Procedure performed as part of RHB-104-01

² Baseline visit should be scheduled once the RHB-104-01 Wk26 / RHB-104-04 Screening CDAI score has been calculated (using RHB-104-01 Wk26 hematoctrit value).

³ Ongoing AEs/ConMeds from RHB-104-01 should be captured in RHB-104-04 eCRF (AEs & ConMeds for RHB-104-01 are captured in -01 eCRF up to day prior to -04 BL)

⁴ The colonoscopy must be performed on or before the Baseline or Week 0 Visit and must not interfere with CDAI data collection. If applicable, biopsies may be collected as part of the RHB-104-01 study.

⁵ In consenting subjects, colonoscopy must be performed up to 14 days after Visit Week 16.

⁶ In consenting subjects, colonoscopy must be performed a minimum of 8 days and a maximum of 20 days prior to visit Week 52.

⁷ IWRS must be accessed to register the assignment & dispensing of an Open-Label start-up kit, following confirmation of eligibility.

⁸ IWRS must be accessed to register the dispensing of an Open-Label maintenance kit.

⁹ CDAI: Subjects will complete a CDAI diary for the 7 full days preceding their next study visit. To ensure compliance, site personnel will contact subjects prior to initiation of the CDAI-recording period, to review the process for adequate CDAI data collection.

¹⁰ ECG: Five minute continuous digital 12-lead ECG after resting 10 minutes in a supine position

¹¹ Urine Testing: Dipstick test only, unless results are abnormal.

¹² Site staff must discuss and review Drug Administration Instructions with subjects, both at drug dispensing and compliance evaluation, during dose escalation.

¹³ Study drug return of maintenance kit #2 bottles (RHB-104-01) and accountability

4.2 Dosage and Administration of Study Drug

The target dose of RHB-104 is 5 capsules administered bid. In order to reach this target with minimal adverse effects, subjects who received placebo during the RHB-104-01 study will be titrated up over the first 4 weeks of treatment, and the dose will remain stable thereafter. Subjects who received RHB-104 will continue to receive RHB-104. In order to maintain blinding in the RHB-104-01 study all subjects will receive 5 blinded capsules bid for the duration of the RHB-104-04 study as detailed below. The study drug will be taken with food. Subjects who fail dose escalation to 5 capsules bid will be considered treatment failures and withdrawn from the study.

Blinded bid Dose Titration and Maintenance Dosing in RHB-104-04 is

		RHB-104-04 START-UP KIT (Weeks 1-4)				MAINTENANCE KITS (Weeks 5-52)
		Weeks				
		1	2	3	4	5-52
BLINDED ACTIVE ARM (ACTIVE + ACTIVE)	RHB-104	Active Daily Dose (mg)				
	Clarithromycin	950mg	950mg	950mg	950mg	950mg
	Rifabutin	450mg	450mg	450mg	450mg	450mg
	Clofazimine	100mg	100mg	100mg	100mg	100mg
		# Capsules Taken (daily)				
	Bottle 1	8 capsules RHB-104	6 capsules RHB-104	4 capsules RHB-104	2 capsules RHB-104	10 capsules RHB-104
	Bottle 2	2 capsules RHB-104	4 capsules RHB-104	6 capsules RHB-104	8 capsules RHB-104	
OR		Active Daily Dose (mg)				
BLINDED PLACEBO ARM (PBO + ACTIVE)	RHB-104	Active Daily Dose (mg)				
	Clarithromycin	190mg	380mg	570mg	760mg	950mg
	Rifabutin	90mg	180mg	270mg	360mg	450mg
	Clofazimine	20mg	40mg	60mg	80mg	100mg
		# Capsules Taken (daily)				
	Bottle 1	8 capsules PLACEBO	6 capsules PLACEBO	4 capsules PLACEBO	2 capsules PLACEBO	10 capsules RHB-104
	Bottle 2	2 capsules RHB-104	4 capsules RHB-104	6 capsules RHB-104	8 capsules RHB-104	

4.3 Subject Number

Subjects will maintain the identification number that was assigned in RHB-104-01.

5. ANALYSIS POPULATIONS

All subjects who signed informed consent will be included in the disposition table counts. The following populations will be used for data analysis.

The Intent-to-Treat (ITT) Population: The ITT population is defined as all subjects who are enrolled in this open-label study and signed the consent form. Efficacy endpoint analyses will be based on ITT population or specified otherwise.

The Safety Population (SAF): The safety population includes subjects who received any amount of study medication. The safety analyses will be based on the SAF population.

6. STATISTICAL METHODOLOGY

6.1 Statistical and Analytical Issues

6.1.1 Statistical Methods

In general, if there is disagreement between this SAP and the statistical methods outlined in the protocol, the SAP would supersede the protocol.

Descriptive statistics summary results will be produced and presented for all the data collected on the different assessments that include demographics, baseline characteristics, concomitant medications, outcome, and safety endpoints. Continuous data summary descriptive statistics will include the number of observations, means, standard deviations, medians, and ranges. Categorical variables will be summarized with frequencies and percentages or specified otherwise.

In the parent study, there was one randomization stratification factor, use of protocol permitted anti-TNF agents (yes/no). In the current study, treatment comparisons will be performed without taking this stratification factor into consideration unless specified otherwise.

All statistical analyses will be performed using SAS statistical software (Version 9.4 or an updated latest higher version available at the time of analysis). Adverse events will be coded using the most recent MedDRA version available at the time of analysis. Concomitant medications will be coded using the most recent version of World Health Organization (WHO) Drug dictionary. The actual version of each dictionary will be footnoted in the respective outputs.

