6.1.7 Determination of Sample Size

This study is anticipated to enroll 100 patients. With that number of patients, a two-sided 95% confidence interval (using the exact Clopper-Pearson method) will have a maximum width of 0.203 (i.e., +/- 10.15%) conservatively assuming the measure of interest has proportion of successes of 50%. This confidence interval will be narrower for any other possible observed proportion.

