6.3.1 Primary Outcome Analysis

The primary outcome variable is the proportion of subjects experienced remission at week 16. 95% exact Clopper-Pearson confidence interval (CI) of the proportion of remission will be provided within each parent study treatment group and overall, as well as subgroup by anti-TNF agent use. Parent study treatment comparison will be performed using Fisher's exact test.

For the above primary analysis, subjects with a missing week 16 CDAI will be treated as not achieving remission. As a sensitivity analyses, the same analyses will be performed without imputation, i.e. subjects with missing week 16 CDAI will not be imputed, therefore it will be missing and excluded from analysis.

Logistic regression modeling will be implemented as additional exploratory analysis to assess relationships between the primary outcomes and putative effect modifiers. The putative effect modifiers include the following patient level biomarker assessment:

- Baseline serum inflammation marker: C-reactive protein (CRP ≥ 2.87 vs. < 2.87 mg/dL)
- Baseline stool inflammation marker: Fecal calprotectin (≥ 250 vs. < 250 mcg/g)
- Baseline SES-CD ≥ 6 , Fecal calprotectin ≥ 250 mcg/g or CRP ≥ 2.87 mg/dL: Yes vs. No

The logistic regression model includes remission at week 16 (yes/no) as a function of parent study treatment by baseline biomarker factor. The aim is to identify if the effect of each baseline biomarker factor has significant effect on remission outcome. The analysis will be performed to compare parent study treatment groups. Odds ratio of remission rate (parent study treatment RHB-104 vs. placebo) and 95% CI will be presented using a Forest plot for each baseline biomarker level. Similar plots will be provided for week 16 response and week 52 remissions.

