6.3.3 Selected Other Secondary Endpoints/Variables

6.3.3.1 Time to Event Endpoints/Variables Analysis

The Time to event endpoints that will be analyzed includes:

- Time to remission
- Duration of remission
- Time to response
- Duration of response

Kaplan Meier survival curves and parameters showing time-to-first observed response outcome will be summarized by parent study treatment, by anti-TNF use and overall. Summary statistics that will be presented will include minimum, maximum, the 25th and 75th percentiles, 95%

confidence intervals on the median (using the method of Brookmeyer and Crowley), and proportion of the events and censored data. Parent study treatment comparison will be performed using log-rank test.

Kaplan-Meier plots with descriptive summary statistics will be presented.

6.3.3.2 Remission from Week 16 through week 52

Number and proportion of subjects experiencing maintenance of remission (CDAI score < 150) from week 16 through week 52 and the number and proportion of subjects experiencing remission at week 16 and week 52 will be provided within each parent study treatment group and overall, as well as subgroup by anti-TNF agent use. 95% exact Clopper-Pearson confidence interval (CI) for the proportion will also be presented. Parent study treatment comparison will be performed using Fisher's exact test.

In addition, similar summaries will be provided for remission at week 52 overall and for subjects who achieved remission at week 16

Proportion of subjects who achieved the following response will be provided overall and by parent study treatment:

Remission at week 16 plus 50% reduction in CRP or calprotectin from baseline

Remission at week 52 plus 50% reduction in CRP or calprotectin from baseline

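### Parent-group comparisons use neither baseline CDAI nor anti-TNF use, so a sizeable baseline CDAI difference could appear as a false gap in remission or, in the opposite direction, in response

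*SAP*

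**What the plan says.** SAP 6.1.1 records that "In the parent study, there was one randomization stratification factor, use of protocol permitted anti-TNF agents (yes/no"), and goes on to say that in this study "treatment comparisons will be performed without taking this stratification factor into consideration unless specified otherwise".

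Nothing later specifies otherwise for the tests. In 6.3.1, for week 16 remission, "Parent study treatment comparison will be performed using Fisher", meaning the exact test. Sections 6.3.2 (week 16 response) and 6.3.3.2 (maintenance of remission) use the same test. For the four time-to-event endpoints in 6.3.3.1, "Parent study treatment comparison will be performed using log-rank test", and no strata are named. The only regression, the exploratory logistic model in 6.3.1, crosses parent treatment with CRP, calprotectin or a composite biomarker category.

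Baseline CDAI is summarised (6.3.4.7) but adjusted for nowhere. Anti-TNF use is not ignored entirely: remission, response, maintenance and Kaplan-Meier results are also displayed by anti-TNF use.

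The protocol admits subjects whose CDAI is still at least 150 after 26 weeks or more of parent study drug. Its statistical section plans no formal group comparison, but SAP 6.1.1 gives the SAP precedence over the protocol.

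**The concern.** Both binary endpoints depend on the starting score. Remission is an absolute threshold: a subject entering at CDAI 160 must fall by more than 10 points, and one entering at 350 by more than 200. Response needs a fall of 100 whatever the start. For the subject at 160 that is much harder than remission, and for the subject at 350 it is much easier.

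Entry depends on an outcome measured after randomisation, in groups that had been on different treatments. Randomisation therefore no longer protects the balance of baseline CDAI or of anti-TNF use. If one parent group enters with higher scores, an unadjusted test can show lower remission and higher response in that group with no difference in the effect of the open-label period. The result could then be read as evidence about earlier exposure to RHB-104.

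**Working it through.** **The plan's own figure.** SAP 6.1.7 says that "This study is anticipated to enroll 100 patients" and that "a two-sided 95% confidence interval (using the exact Clopper-Pearson method) will have a maximum width of 0.203", "conservatively assuming the measure of interest has proportion of successes of 50"%. Clopper-Pearson limits for 50 of 100, from beta quantiles, are 0.3983 and 0.6017. The width is 0.2034, so the figure reproduces. It concerns one overall proportion. No power is stated for a group comparison.

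**Assumptions not in the documents.** 50 subjects per parent group. Baseline CDAI (B) normal with SD 75, cut off below 150. Week 16 CDAI = 150 + s(B − 150) − 10 + N(0, 70²), with no group effect. The slope s is how strongly baseline predicts week 16.

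With x = B − 150:
- P(remission) = Φ((10 − s·x)/70), which falls as x rises when s > 0.
- P(response) = Φ(((1 − s)·x − 90)/70), which rises as x rises when s < 1.

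Example with s = 0.6:
- B = 160 (x = 10): remission Φ(4/70) = 52%, response Φ(−86/70) = 11%.
- B = 350 (x = 200): remission Φ(−110/70) = 6%, response Φ(−10/70) = 44%.

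**False-positive rate of Fisher's test.** Averaging these probabilities over each group's baseline distribution gives rates p1 and p2. The rejection rate is the sum of Bin(i; 50, p1)·Bin(j; 50, p2) over all tables with two-sided p ≤ 0.05. Underlying means of 235 vs 265 become 253 vs 275 after the cut at 150 (modest imbalance); 220 vs 280 become 243 vs 287 (large).

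| s | Imbalance | Remission, lower vs higher group | Fisher rejects | Response, lower vs higher group | Fisher rejects |
|---|---|---|---|---|---|
| 0.3 | modest | 38.7% vs 35.3% | 4.1% | 40.9% vs 48.3% | 8.7% |
| 0.3 | large | 40.2% vs 33.5% | 7.3% | 37.6% vs 52.4% | 26.4% |
| 0.6 | modest | 25.8% vs 21.1% | 5.5% | 25.5% vs 29.6% | 4.8% |
| 0.6 | large | 28.0% vs 18.8% | 14.0% | 23.8% vs 31.9% | 10.6% |

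With no imbalance, Fisher's actual size at these two slopes is 3.0–3.4%. A logistic likelihood-ratio test adjusted for baseline CDAI rejects in 4.6–6.7% across the same eight cells (4,000 simulated trials each).

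Outside these slopes the bias shifts to one endpoint. At s = 0 remission is Φ(10/70) = 56% in both groups, and the whole imbalance goes into response.

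**A second set of assumptions agrees for remission.** Baseline mean 260, SD 70, cut at 150; residual SD 90; 30% anti-TNF users whose week 16 CDAI is 30 points higher. A 40-point shift in the underlying mean (about 34 after the cut) gives:

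| s | Remission | Fisher rejects |
|---|---|---|
| 0 | 33% vs 33% | 3.0% |
| 0.3 | 33% vs 29% | 3.9% |
| 0.6 | 33% vs 26% | 7.9% |
| 0.9 | 34% vs 24% | 13.5% |

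The adjusted model rejects in 4.8–6.1%. A 20-point shift leaves Fisher at or below 5%.

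**Power with balanced baselines.** Under the second set, with true remission rates of about 33% vs 53–57%:

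| s | Fisher | Unadjusted likelihood ratio | CMH by anti-TNF | Adjusted for CDAI and anti-TNF |
|---|---|---|---|---|
| 0 | 59% | 67% | 66% | 66% |
| 0.3 | 58% | 65% | 64% | 67% |
| 0.6 | 54% | 61% | 60% | 65% |
| 0.9 | 46% | 55% | 53% | 62% |

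The covariates add between nothing and 7 points over the unadjusted likelihood-ratio test (62 − 55 = 7 at most). The step from Fisher to that test is 7 to 9 points and reflects only the conservatism of the exact test. Stratifying by anti-TNF alone adds nothing at assumed effects of 30 to 60 CDAI points. At 120 points (s = 0.3) it adds about 5 points with 30% users and 9 with 50%.

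**The case against.** The strongest reply is that these comparisons are not what the study is for. The primary objective is to estimate one remission rate, the sample size rests on the precision of that rate, and the protocol planned no formal group comparison. The omission of anti-TNF is stated openly and results are still shown by anti-TNF use. CDAI is tabulated by visit, so a baseline imbalance should be visible. All of this stands. It limits the weight of the point, but a subgroup display does not adjust a comparison.

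Three stronger readings are tempting and are not supported.
- A reader might infer that any baseline CDAI difference becomes a remission difference. It does so only as far as baseline predicts week 16, and a modest shift leaves the remission test near nominal.
- A reader might infer that, because the parent trial was stratified by anti-TNF use, leaving it out costs material power. This cohort is no longer the randomised one, and no gain is shown unless anti-TNF use is strongly prognostic, on which the documents are silent.
- A reader might credit the whole difference between Fisher and an adjusted model to the covariates. In most of the scenarios above, half or more of it is Fisher's conservatism.

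It is also fair that baseline CDAI was measured after parent treatment and may carry part of its effect. Adjusting for it changes the question and does not restore a randomised comparison.

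**Conclusion.** The concern holds for the non-primary parent-group comparisons only. They leave out the variable that decides entry and on which both binary endpoints depend. With 50 per group and slopes of 0.3 and 0.6, Fisher's false-positive rate is about 4–9% for a modest baseline imbalance and about 7–26% for a large one, against about 3% with none. Remission and response are pushed in opposite directions. The adjusted test stays close to 5%.

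The group split, the CDAI spread, the imbalance and the link between baseline and week 16 are all assumed, and no document shows that an imbalance exists. The power argument is weak: about 0 to 7 points from the covariates when anti-TNF use is at most moderately prognostic. The overall remission rate and its exact confidence interval are unaffected. The change is worth making because it costs almost nothing.

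**What to change.** For each parent-group comparison that is kept:
- **SAP 6.3.1 to 6.3.3, binary endpoints:** add a logistic model of remission or response on parent group, continuous baseline CDAI and anti-TNF use. Report the adjusted odds ratio and risk difference with 95% CIs. The planned Fisher test can stay beside it.
- **SAP 6.3.3.1, times to event:** add a Cox model with the same covariates, or a log-rank test stratified by anti-TNF use.
- **SAP 6.1.1:** amend the sentence on the stratification factor so that it allows these analyses, and state whether anti-TNF use means the parent stratum or use at entry.
- **Labelling:** call the results exploratory and conditional on entry severity, and say that adjustment does not restore a randomised comparison.

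The cost is some SAP wording and a few lines of code on variables already held. The downside is a little more analysis and an adjusted estimate that answers a conditional question, which readers must be told.
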